1. SYNOPSIS

Trial title	A phase IV, single-blinded, prospective,	
	randomized, controlled, multi-center study to	
	compare the clinical outcomes of GERI+ time	
	lapse system with a conventional embryo culture	
	and assessment system	
Trial number	MS200497_0006	
Sponsor	Merck KGaA, [name]	
Trial type	Phase IV company sponsored trial	
Coordinating Investigator	TBC	
Trial center(s)/country(ies)	16 Centers in 7 Countries:	
	Italy, Spain, Portugal, France, Denmark, Norway,	
	Canada	
Study duration	21 months recruitment time + 3 months	
	observation time = 24 months from FPI (First	
	Patient In) until LPO (Last Patient Off study)	
Trial objectives	The main objective of this trial is to evaluate the	
	overall clinical value of GERI+ as an integrated	
	embryo culture and assessment system, providing	
	an undisturbed culture environment, continuous	
	monitoring of embryo development and automated	
	scoring using a predictive algorithm.	
Trial design and plan	Single-blinded, prospective, randomized,	
	controlled, multicenter trial with two treatment	
	arms.	
	No interim analysis is planned.	
Planned number of subjects	1,386	
Study population	IVF/ICSI patients	
Main inclusion and exclusion	-	
criteria	1. Couples with ≤ two failed fresh IVF/ICSI	
	embryo transfer cycles.	

Protocol Version: 3.0 / Jan 31, 2018 10 / 49

trial

	2. Age ≥ 18 and ≤ 40 years	
	3. BMI: 18-30 kg/m ²	
	4. Normal uterine cavity under ultrasound.	
	5. Subject and her husband/partner must have	
	read and signed the Informed Consent form.	
	6. At least four normally fertilized oocytes (2PN)	
	in the current cycle.	
	Exclusion:	
	1. Male with non-ejaculated sperm	
	2. Subjects with abnormal, undiagnosed	
	gynecological bleeding or with genitourinary	
	malformations.	
	3. Subjects with any contraindication to COS for	
	ART or to gonadotropins.	
	4. Planned "freeze all" cycle (oocytes or	
	embryos).	
	5. Planned PGS or PGD cycle.	
	6. Concurrent participation in another clinical	
	study.	
Investigational Medicine	Not applicable.	
Product		
Investigational Medical	GERI+ incubator equipped with EEVA and GERI	
Device	Assess software.	
Planned duration of	10-12 weeks.	
observation for each subject		
Primary endpoint(s)	Clinical pregnancy with positive fetal heart beat in	
	gestational week 6-8 after fresh embryo transfer on	
	Day 3.	
Secondary endpoint(s)	1. Number of utilizable embryos	
	2. Number of good quality embryos	
	3. Number of non-viable embryos	
	4. Implantation with positive fetal heart beat	
	5. Biochemical pregnancy	
	6. Ongoing pregnancy	

Protocol Version: 3.0 / Jan 31, 2018 11 / 49

Study Number: MS200497_0006 trial

	7. Multiple pregnancy8. Ectopic pregnancy	
	9. Spontaneous miscarriage	
Estimated Trial calendar	FPI: April 2018	
	LPI: December 2019	
	LPO: March 2020	
	Trial Report Date: October 2020	

Protocol Version: 3.0 / Jan 31, 2018

trial

3. BACKGROUND INFORMATION

Embryo incubators equipped with function of continuous time-lapse (TL) imaging have been widely used in IVF laboratories. However, there is still a lack of consolidated evidence to ascertain whether embryos cultured in an undisturbed environment and assessed by TL images in combination with predictive algorithm may yield superior clinical outcomes than those cultured in conventional incubators and evaluated by benchtop microscopes (Armstrong et al., 2015a; Armstrong et al., 2015b). In general, there are two potential benefits of TL incubators:

A. The undisturbed embryo culture conditions

When cultured in conventional incubators, the embryos of a patient are usually taken out from the incubator and examined at least twice with the bench-top microscopy for Day 3 fresh embryo transfer, the first time on Day 1 for fertilization check, and the second time on Day 3 for cleavage-stage embryo viability assessment (Alpha Scientists in Reproductive Medicine and ESHRE Special Interest Group Embryology, 2011). If the embryos of more than one patients are stored in one conventional box incubator, the exposure of embryos to external environment caused by the frequent opening of incubator doors are even more. Such disturbance to the homeostatic temperature and pH conditions has been proved to be detrimental to the growth of embryos (Zhang et al., 2010).

A recent single-center RCT showed that embryos cultured in EmbryoScope (Vitrolife, Sweden), a box TL incubator, showed no benefit in clinical outcomes over those cultured in conventional box incubators (Park et al., 2015). This might be explained by the fact that culturing of embryos of multiple patients in one big chamber may inevitably lead to lid openings disturbing the culture conditions. In contrast, TL incubators such as GERI (Genea Embryo Review Instrument, Genea Biomedx, Australia) and GERI+ (Genea Biomedx, Australia) are equipped with both microscopes/cameras and independent incubation chamber for each individual patient, providing undisturbed homeostatic conditions throughout the culture period. High-level evidence is needed to confirm whether undisturbed culture conditions, as provided by GERI or GERI+ incubators, may contribute to the optimal growth of embryos.

B. The continuous monitoring of embryos

The conventional method for embryo assessment developed in 1980s is based on daily observations of embryos under regular epi-light microscopy (Fisch et al., 2001; Scott, 2003). This system relies on the static images of embryos analyzing the cell numbers, symmetry of the blastomeres, multinucleation, fragmentation, vacuoles, and etc. (Alpha Scientists in Reproductive Medicine and ESHRE Special Interest Group Embryology, 2011). Due to the limited number of images examined, the predictive value of such embryo assessment system is very limited, as elaborated in detail below:

- 1) The status of embryo fragmentation and multinucleation are usually highly dynamic (Bromer and Seli, 2008).
- 2) Irregular divisions such as direct cleavage (i.e. division from one cell to three cells) (Athayde Wirka et al., 2014) and reverse cleavage (fusion of two cells) (Liu et al., 2014) are hallmarks of embryos of poor quality but cannot be captured by conventional microscopic observation.
- 3) Studies showed that cell number and morphology of approximately 50% of the embryos may change within 4 hours from 38 to 42 h post insemination, resulting in alternations in their assessment (Bromer and Seli, 2008; Montag et al., 2011).
- 4) Embryo assessment only by Day 3 morphology does not necessarily reflect the viability and developmental potential of the embryo (Milki et al., 2002; Rijnders

Protocol Version: 3.0 / Jan 31, 2018 14 / 49 and Jansen, 1998).

The GERI Assess software embedded in the GERI+ system facilitates the identification of the irregular divisions and recording of the developmental timing and cell numbers at different developmental stages by continuous TL imaging. Again, evidence is needed to prove whether such objective and continuous assessment of embryos will lead to better clinical outcomes.

EEVA (Early Embryo Viability Assessment) is an automated embryo prognostic software. It analyzes the dark-field images obtained through a GERI+ incubator and assesses the embryo quality automatically based on morphokinetic parameters and morphology (VerMilyea et al., 2014; Wong et al., 2010). There is also another embryo assessment model based on morphokinetic parameters (Rubio et al., 2014). However, a well-accepted universal empirical algorithm is currently unavailable. The benefit of embryo assessment based on morphokinetics is still in debate and contradicting results have been reported in several single-center RCTs using different algorithms (Adamson et al., 2016; Armstrong et al., 2015b; Basile et al., 2015; Goodman et al., 2016).

In this multi-centric, single-blinded, randomized and controlled trial we will investigate whether embryos cultured under the undisturbed conditions and assessed with continuous monitoring of morphological and morphokinetic parameters may lead to better clinical outcomes as compared to embryos cultured in conventional incubators and assessed by bench-top microscopy. The main aim of this trial is to evaluate the overall clinical value of GERI+ as an integrated embryo culture and assessment system, providing an undisturbed culture environment, continuous monitoring of embryo development and automated scoring using a predictive algorithm.

4. BENEFIT-RISK ASSESSMENT

The GERI+ system is composed of the following two components:

- 1) GERI+ embryo incubator, a CE marked Class IIA medical device.
- 2) EEVA automated embryo prognosticsoftware, a CE marked Class IIA/B medical device.

Protocol Version: 3.0 / Jan 31, 2018

Study Number: MS200497_0006

[figure not shown]
trial

The analysis of the risks and benefits demonstrated that, the GERI+ system met its safety and performance requirements and the device fulfilled its intended use as claimed by Genea Biomedx, the manufacturer of GERI+ incubator, in the CE certificate. In addition, Merck KGaA confirms that the GERI+ incubator and EEVA system comply with the Essential Requirements of the European directives 93/42/EEC (Medical Device Directive). Following is a description of potential risks and expected benefits that may be associated with the use of GERI+ system.

4.1 Risks Related to the GERI+ system

There is a potential risk to embryonic viability brought about by suboptimal culture conditions. The GERI+ incubator minimizes the risks that might potentially impact the embryo survival and growth as GCI

EEVA is a medical device prognostic software used adjunctively with conventional

Protocol Version: 3.0 / Jan 31, 2018 16 / 49

morphological assessment, and no risk is expected for clinical use of EEVA in embryo assessment.

4.2 Benefits of the GERI+ system

The GERI+ system provides undisturbed and comparable embryo culture conditions to the conventional embryo culture system.

Adjunctive use of the EEVA prognostic test (early version with 2 EEVA categories, High and Low) has been shown to significantly improve the ability to identify embryos that would reach the usable blastocyst stage, with a specificity of 84.7% (52% for morphology alone) and a positive predictive value (PPV) of 54.7% (34.5% for morphology alone) (Conaghan et al., 2013). Specificity (or true negative rate) is the percentage of embryos that have a negative "test" result ("EEVA Low") and a negative outcome (non-usable blastocyst). The EEVA test also reduced inter-embryologist specificity variability in embryo assessment (Conaghan et al., 2013). The value of EEVA in predicting blastocyst formation and improving consistency of embryo assessment was later reconfirmed in a prospective multicenter study (Diamond et al 2015). Quite recently, Adamson et al (2016), in a prospective concurrent controlled trial comparing adjunctive use of EEVA (version 2.0, with 2 EEVA categories, High, and Low) against conventional morphology alone, showed significantly higher Day 3 implantation (30.2% vs 19.0%) and clinical pregnancy rates (46.0 vs 32.1%) in the 2 groups respectively (Adamson et al., 2016). They conclude that this non-invasive test adds valuable information to conventional morphological assessment (Adamson et al., 2016; Diamond et al., 2015).

An additional benefit is that the GERI+ system generates consistent and objective data that help embryologists to standardize embryo assessment between embryologists and IVF clinics (Adamson et al., 2016; Diamond et al., 2015). The subjects included in this trial may also benefit from the GERI+ system by getting more viable embryos with high implantation potential for transfer.

5. STUDY OBJECTIVES AND ENDPOINTS

5.1 Objectives

The main aim of this trial is to evaluate the overall clinical value of GERI+ as an

Protocol Version: 3.0 / Jan 31, 2018 17 / 49

Study Number: MS200497_0006

trial

integrated embryo culture and assessment system, providing an undisturbed culture environment, continuous monitoring of embryo development and automated scoring using a predictive algorithm

5.2 Endpoints

5.2.1 Primary Endpoint

The primary end point is clinical pregnancy with fetal heartbeat. It is defined as the pregnancy diagnosed by ultra-sonographic or clinical documentation of at least one fetus with heart beat in gestational week 6 to 8. It includes ectopic pregnancy (Zegers-Hochschild et al., 2009).

.

5.2.2 Secondary Endpoints

- The number of Utilizable Embryos: defined as the number of embryos that are transferred and/or cryopreserved per subject.
- The number of Good Quality Embryos: defined as the number of embryos with 7 or more blastomeres, <25% fragmentation, size and symmetry of blastomeres appropriate to the cell number, and no evidence of multinucleation, based on the morphology on Day 3 of embryo culture per subject (modified from Alpha Scientists in Reproductive Medicine and ESHRE Special Interest Group Embryology, 2011).
- The number of Non-viable Embryos: defined as the number of embryos in which development has been arrested for at least 24 h or in which all the cells have degenerated or lysed (Alpha Scientists in Reproductive Medicine and ESHRE Special Interest Group Embryology, 2011).
- Implantation with positive fetal heart beat: Implantation refers to the attachment and subsequent penetration by the zona-free blastocyst (usually in the endometrium) that starts 5 to 7 days after fertilization (Zegers-Hochschild et al., 2009). A successful implantation is defined as the presence of one gestational sac with fetal heart beat under ultrasonography at gestational weeks 6-8.
- Biochemical Pregnancy: defined as a pregnancy diagnosed only by the detection of hCG in serum or urine and that does not develop into a clinical pregnancy (Zegers-Hochschild et al., 2009).
- Ongoing Pregnancy: defined as the presence of viable fetuses identified by ultrasonography at gestational weeks 10-12 (Rubio et al., 2014).

Protocol Version: 3.0 / Jan 31, 2018 18 / 49

Study Number: MS200497_0006

[figure not shown]
trial

• Multiple Pregnancy: defined as a pregnancy with more than one fetus. It is identified by ultrasonography at gestational weeks 10-12 (Zegers-Hochschild et al., 2009).

- Ectopic Pregnancy: defined as a pregnancy in which implantation takes place outside the uterine cavity. It is identified by ultrasonography at weeks 6-8 (Zegers-Hochschild et al., 2009).
- Spontaneous Miscarriage: the spontaneous loss of a clinical pregnancy before 20 completed weeks of gestational age (18 weeks after fertilization) (Zegers-Hochschild et al., 2009). In this study, the spontaneous miscarriage is tracked up to 10-12 weeks of gestational age.

6. INVESTIGATIONAL PLAN

6.1 Overall Study Design and Plan

This is an interventional, multi-center, single-blinded (the subjects are blinded while the clinicians and the embryologists are not blinded), randomized, controlled clinical trial and will include 16 investigational sites. Each site will conduct the trial using the same clinical protocol. Recruitment of subjects at each site, with subjects who voluntarily consent to participate, is expected to continue for up to 21 months. Competitive enrollment is applied to maximize subject recruitment. Additional follow-up after embryo transfer will take place up to 12-18 days to verify hCG positivity, at 6-8 gestational weeks to verify implantation and clinical pregnancy, and 10-12 gestational weeks to verify ongoing pregnancy. Total duration of the trial, including start up (First patient in, FPI) and close out activities (Last patient off study, LPO), is approximately 24 months.

trial

6.2 Discussion of the Study Design

The design selected for this trial is defined based on the need to locally validate the value of GERI+ system to improve clinical outcomes by collecting real life clinical data. It will be the first multi-centric RCT to be implemented in Europe testing the potential benefit brought about by the GERI+ integrated embryo culture and EEVA assessment system over conventional embryo culture and microscopy-based static morphological assessment method. Considering the large sample size, it will also be a landmark for the future application of this integrated continuous monitoring and undisturbed embryo culture and assessment system worldwide.

The rate of clinical pregnancy with positive fetal heart beat (CPR with positive FHB) will be studied in this trial as the primary endpoint. CPR with positive FHB provides strong evidence for continued viability of embryos, following culture and assessment.

This trial is single-blinded for subjects and is open to embryologists who will process, culture and grade the embryos, and to clinicians/nurses who will perform the embryo transfer and pregnancy tests and scans. Considering the volume of IVF and ICSI patients in these 16 sites participating in this trial, recruitment of subjects should be completed within 21 months.

6.3 Inclusion of Special Populations

Not applicable.

6.4 Enrollment of Trial Population

All subjects must meet all the inclusion criteria and must not meet any of the exclusion criteria.

6.4.1 Inclusion Criteria

- 1) Couples with \leq two failed fresh IVF/ICSI embryo transfer cycles.
- 2) Age \geq 18 and \leq 40 years.
- 3) BMI: $18-30 \text{ kg/m}^2$.
- 4) Normal uterine cavity under ultrasound.
- 5) Subject and her husband/partner must have read and signed the Informed

Protocol Version: 3.0 / Jan 31, 2018 20 / 49

trial

Consents form.

6) At least four normally fertilized oocytes (2PN) in the current cycle.

6.4.2 Exclusion Criteria

- 1) Male with non-ejaculated sperm.
- 2) Subjects with abnormal, undiagnosed gynecological bleeding or with genitourinary malformations.
- 3) Subjects with any contraindication to COS for ART or to gonadotropins.
- 4) Planned "freeze all" cycle (oocytes or embryos).
- 5) Planned PGS or PGD cycle.
- 6) Concurrent participation in another clinical study.

6.5 Recruitment of Participants

Subjects will be recruited from patients undergoing IVF or ICSI treatment cycles at the investigators' clinics. Subjects will be assessed according the Inclusion/ Exclusion criteria to determine their eligibility.

6.6 Method of Blinding

- Blinding: The trial is blinded to the subjects. The trial is not blinded to the embryologists handling the embryos or the clinicians/nurses conducting embryo transfer and pregnancy tests/scans.
- Emergency Un-blinding: in case of a medical emergency, the subject will be informed by her trial doctor or embryologist which incubator and embryo grading method are used for her embryos.

6.7 Randomization and Allocation of Subjects

After signing the informed consent form, all eligible subjects will be randomized and allocated to either of the two treatment groups immediately after fertilization check on Day 1 of embryo culture.

A stratified block randomization with fixed block length and allocation ratio 1:1 will be used. The stratification will be based on site and the age of subject (age group 18-35 vs. 36-40). Randomization will be accomplished using the Interactive Web Response Services (IWRS) system. An independent statistician will generate the

Protocol Version: 3.0 / Jan 31, 2018 21 / 49

Study Number: MS200497_0006

randomization schedule and upload to the IWRS system. All randomization codes will not be reused and subjects who discontinue the study early will not be replaced.

A subject can be considered as a drop-out during the study if she is randomized but primary endpoint data is not available for this subject, for whatever reason. Reasons for study discontinuation will be recorded in the Trial Exit eCRF.

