8.2 Randomization

A stratified permutated block randomization with fixed block size and allocation ratio 1:1 will be used. Randomization will be accomplished using Interactive Web Response Services (IWRS) system. The stratification will be based on site and age of the subject (18-35 versus 36-40). This guarantees, at any time, a similar number of subjects between experimental and control groups at each site.

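### One fixed block length within site-by-age strata, with site staff unblinded, lets some allocations be foreseen: a preventable selection-bias risk, not a shown bias

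*Protocol*

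**What the plan says.** Protocol section 6.7 sets the scheme: "A stratified block randomization with fixed block length and allocation ratio 1:1 will be used". Section 8.2 repeats it: "A stratified permutated block randomization with fixed block size and allocation ratio 1:1 will be used". The strata are given in section 6.7: "The stratification will be based on site and the age of subject (age group 18-35 vs. 36-40"). Section 6.1 says that the trial "will include 16 investigational sites", with recruitment lasting up to 21 months under competitive enrolment.

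On blinding, section 6.6 says: "The trial is not blinded to the embryologists handling the embryos or the clinicians/nurses conducting embryo transfer and pregnancy tests/scans". Only the women are blinded.

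Several safeguards are stated:
- An independent statistician prepares the schedule, and "Randomization will be accomplished using the Interactive Web Response Services (IWRS) system" (section 6.7).
- Consent is to be signed before oocyte retrieval (section 9.2).
- Randomisation follows at once after the Day 1 count of normally fertilised (2PN) oocytes (sections 6.7 and 7.3).

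Neither document gives the block length, mentions varying it, or says that it is withheld from sites.

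**The concern.** A central system protects the list itself. It does not protect the next allocation if that can be worked out from earlier ones. Here each stratum uses one constant block length, and the people who culture, grade and transfer the embryos know which incubator each woman's embryos went into. A site can keep a tally for each of its two age groups, infer the length, and then know the closing allocations of each block.

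If that knowledge influenced who entered next, prognosis would become linked to arm within strata. The Cochran-Mantel-Haenszel test in Protocol section 8.4.2 adjusts for the stratification factors, so it would not remove an imbalance arising inside a stratum. SAP section 7 drops between-group comparisons and regression models, but descriptive pregnancy rates by arm would carry the same bias.

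**Working it through.** **1. The plan's own figure.** Protocol section 8.1 assumes 30% against 37.5% (a 25% relative increase), two-sided alpha 0.05 and 80% power. With the pooled-variance formula,

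n = [1.960 × √(2 × 0.3375 × 0.6625) + 0.842 × √(0.30 × 0.70 + 0.375 × 0.625)]² / 0.075² = 622.8, so 623 per group.

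623 / 0.9 = 692.2, so 693 per group and 1,386 in all. The sample size reproduces and is not in dispute. The planned effect is 7.5 points.

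**2. Allocations that are certain.** In a 1:1 permuted block of known length b, the expected share of allocations fixed by those already made is 1 / (b/2 + 1). For b = 4, the last allocation is always certain, and the third is too when the first two match (probability 1/3). That gives (1 + 1/3) / 4 = 1/3. The best-guess rate comes from always naming the arm that is behind in the block. The lengths below are assumptions, because the documents give none.

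| Block scheme | Certain | Of 1,386 | Best guess correct |
|---|---|---|---|
| Fixed 4 | 33.3% | 462 | 70.8% |
| Fixed 6 | 25.0% | about 347 | 68.3% |
| Fixed 8 | 20.0% | about 277 | 66.6% |
| Varying 4/6/8 | about 2.3% | about 32 | about 67.7% |

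The fixed rows assume that the length is known from the first woman in each stratum, so they are ceilings. The last row is a simulation of an optimal guesser who knows the set of lengths but not their order.

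**3. Ease of keeping a tally.** 16 sites × 2 age groups = 32 strata. 1,386 / 32 is about 43 women per stratum, and 43 / 21 months is about 2 a month. These are averages, since enrolment is competitive.

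**4. Upper bound on bias.** Assume that women steered into certain slots differ between arms by 3 to 9 points in pregnancy chance (no source in the documents), and that steering happens in every certain slot. With block 4, the bias is 0.333 × (3 to 9) = 1 to 3 points.

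**5. Same-day order of entry.** This route needs no bending of eligibility, but it works only between women in the same site and age stratum on the same day. Assume that fertilisation checks are spread at random over about 450 working days.
- Average enrolment (43 per stratum): the share with a same-day stratum-mate is 1 − (1 − 1/450)^42 = 8.9%. One third of these are in a certain slot, so 3.0%. Bias: 0.030 × (3 to 9) = about 0.1 to 0.3 points.
- Three times that (about 130 per stratum): 1 − (1 − 1/450)^129 = 24.9%, and one third is 8.3%. Bias: 0.083 × (3 to 9) = about 0.25 to 0.75 points.

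Clustered retrieval days would raise these figures.

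**6. Effect on a 5% test, if one were run.** With 30% in both arms and 623 per group, the standard error is √(2 × 0.30 × 0.70 / 623) = 2.6 points. Shifting the normal statistic by bias / 2.6 gives a two-sided type I error of about 5.0-5.2% for a bias of 0.1 to 0.3 points, 6.0% for 0.75 points, and 7% to 21% for the 1 to 3 point upper bound.

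**The case against.** The strongest case against is that the stated procedures leave little room for steering. Consent comes before retrieval, the last eligibility criterion (at least four 2PN oocytes) is known only on Day 1, and randomisation then follows at once. When a couple consents, staff cannot be sure which slot they will fill. The list is prepared by an independent statistician and issued centrally, and the block length is not printed. The SAP (section 10.1) also reports screened and screen-failed women, which offers some view of selective entry.

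Most of this stands, and it is why the same-day figures are small. It narrows the routes without closing them. Besides order of entry, there remain the choice of whom to approach, the 2PN judgement near the threshold of four, and the declaration of a planned freeze-all cycle. A constant length can be inferred even if it is never disclosed.

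A second objection is that varying the blocks hardly changes how often a good guess succeeds. That is correct: about 68% with 4/6/8, against 70.8% with fixed 4 and 66.6% with fixed 8. The gain lies in the certain slots.

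A reader might also infer that unblinded embryologists and clinicians run the randomisation. The documents do not support that. The schedule is central, and they do not say who triggers the request. That site staff can see past allocations follows from the open handling of embryos in section 6.6; it is not stated.

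**Conclusion.** The point holds as a preventable design risk. Fixed-length blocks within site-by-age strata, with unblinded site staff, leave 33%, 25% or 20% of allocations certain in advance for blocks of 4, 6 or 8, provided that the length is known or inferred.

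A reader might take 1 to 3 points as the expected bias, or conclude that the comparison is biased. The documents support neither reading. The larger figure requires steering in every certain slot, and nothing shows that any steering occurred. By same-day order alone, the size is about 0.1 to 0.3 points at average enrolment and up to about 0.75 at three times that, against a planned effect of 7.5. These values rest on block 4, a 3 to 9 point prognostic difference, and entry spread at random over about 450 working days. The other routes cannot be sized from the documents.

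**What to change.** In Protocol sections 6.7 and 8.2, replace the fixed block length and size with randomly varying block sizes (for example 4, 6 and 8), and state that the sizes are withheld from sites and study staff. The independent statistician and the central web system stay as they are.

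The cost is one regenerated list and a line in each of two sections; the sample size stays at 1,386. The imbalance at the end of a stratum can be slightly larger: at most 4 with a largest block of 8, against at most 2 with fixed blocks of 4. The aim in section 8.2 of similar numbers per arm at each site is still broadly met. If a lower best-guess rate is also wanted, fewer strata or a less restrictive scheme would be needed.

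The change helps only women not yet randomised. The Synopsis plans the last patient in for December 2019, and the current SAP is dated 14 January 2020. If that calendar held, the change comes too late for this trial, and the report can only disclose the scheme and block length as a limitation.
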